# 7.3.7 REPORTING PROCEDURE TO ETHIC COMMITTEES (EC) AND TO REGULATORY AUTHORITIES

The Investigator shall report all serious adverse events immediately to Dompé Pharmacovigilance. The Investigator shall notify SAE to his/her EC as applicable; in addition, for reported deaths of a subject, the Investigator shall supply Dompé Pharmacovigilance and the Ethics Committee with any additional information requested. Copies of all correspondence relating to reporting of any SAEs to the EC should be maintained in the Investigator's Files. Dompé Pharmacovigilance shall submit any serious unexpected ADR (SUSAR) to the concerned EC and Regulatory Authority (via Eudravigilance) which approved the study, as soon as possible and in no event later than:

- seven calendar days after becoming aware of the information if the event is fatal or life threatening; to be followed by any relevant information within eight days.
- fifteen calendar days after becoming aware of the information if the serious event is neither fatal nor life threatening.

Dompé Pharmacovigilance shall report any relevant updated follow-up safety information as soon as available.

If the results of an investigation show that an ADR not initially determined to be reportable is reclassified as reportable, Dompé Pharmacovigilance shall report such reaction in a written safety report as soon as possible, within the timeframes defined by current law requirements.

Dompé shall be responsible to prepare and submit annual safety reports (Development Safety Update Report – DSUR) to relevant Regulatory Authorities, as applicable. In addition, Investigator will receive from Dompé Pharmacovigilance appropriate periodic safety updates, as per applicable local requirements and regulations.

# 7.3.8 EXPOSURE TO INVESTIGATIONAL PRODUCT DURING PREGNANCY

Women of childbearing potential are not excluded from the study as long as adequate birth control methods are being utilized. Women of childbearing potential are defined as all women physiologically capable of becoming pregnant. Prior to enrolment in the clinical trial, female patients of childbearing potential and their partners must be advised of the importance of avoiding pregnancy during the entire course of the study treatment and for the 30 days after the study treatment period ends and of the potential risks associated with an unintentional pregnancy. During the trial, female patients are to be instructed to contact the Investigator immediately if they suspect they might be pregnant. In the same way, male patients who become aware that the partner might be pregnant, are to be instructed to contact the Investigator immediately.

The Investigator must report every pregnancy on a pregnancy report form as soon as possible (within 24 hours of learning of the pregnancy to Dompé Pharmacovigilance (contacts specified in the section "Contact Information"), even if no AE has occurred, and follow it to term. If, however, the pregnancy is associated with an SAE (eg, if the mother is hospitalized for dehydration), in addition to the pregnancy report form, a separate SAE report form must be filed as described in Section 7.3.6, with the appropriate serious criterion (eg, hospitalization) indicated on the SAE report form. Miscarriage, stillbirth and any malformation/disease must be reported as a SAE.

Any pregnancy leads to the immediate exclusion from the trial.

## 7.3.9 ADVERSE EVENTS CAUSING TREATMENT DISCONTINUATION

If a patient is withdrawn from the study as a consequence of an AE, this must be recorded and reasoned in the CRF, and the patient must be followed up until the resolution of the AE or as instructed by the medical monitor.

## 7.3.10 OVERDOSE

Cases of overdose (accidental or intentional) which may or may not result in serious adverse reactions are to be reported to Dompé Pharmacovigilance and Dompé Medical Expert, following the same

procedure for SAE, within 24 hours from the Investigator's knowledge of its occurrence. The Medical Expert should be contacted to discuss corrective treatment, if necessary. An overdose of the study drug is defined as:

- Tablets: The administration of 3 or more additional tablets on any given treatment day

- IV formulation: The administration of more than 50% of the daily dose.

Overdose includes reports related to drug intake through different routes (e.g. ingestion) or with suicidal intentions and consequent drug overdose.

The Investigator shall provide in the SAE form information about symptoms, corrective treatment and outcome of overdose.

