# - Safety Endpoints:

- Adverse events
- Serious adverse events

**Procedures and Assessments:** Efficacy and Safety procedures and assessments for this study will include all the listed enpoints as well as the recording of concomitant medications' use.

**Overall Study Design:** this clinical trial is designed as an adaptive, randomized, controlled, multicentre study to evaluate efficacy and safety of Reparixin in hospitalized adult patients with severe COVID-19 pneumonia. In the phase 2 segment of this study, patients will be randomized 2:1 to Reparixin oral tablets 1200 mg (Group 1, active treatment) or standard of care (Group 2, control arm). In case of worsening (e.g. need of ICU and/or mechanical ventilation) after the first 24hrs, patients will be offered a rescue medication based on their physicians' judgement, without any constrain from the sponsor. The administration of rescue medications is allowed, without constituting a protocol deviation. In the phase 3 segment of this study, it is planned that patients will be randomized 2:1 to Reparixin or standard of care. In case of worsening after the first 24hrs, patients under the control arm will be offered a rescue medication with the active treatment (Reparixin 1200 mg oral tablets TID) or Reparixin 2.772 mg/kg body weight/hour IV infusion, if the oral route is unfeasible for the clinical condition. The Phase 3 design will be reassessed and decided based on the results of the Phase 2.

**Population:** Hospitalized adult ( $\geq$ 18 <90 years old) patients with severe COVID-19 pneumonia. No gender and/or ethnicity restrictions will apply.

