### 4 STUDY DESIGN AND METHODOLOGY

#### 4.1 Phase 2 Study design

The study is designed for the investigational use of a CXCR1 and CXCR2 allosteric antagonist named Reparixin. It will involve 48 adult patients with severe COVID-19 pneumonia in accord with any of the following:

1. Age 18 to 90.

2. Confirmed COVID-19 diagnosis

3. At least one of the following: (1) Respiratory distress,  $RR \ge 30$  breaths/min without oxygen; (2) Partial arterial oxygen pressure (PaO2) / Fraction of inspiration O2 (FiO2) >100 <300mmHg (1mmHg = 0.133kPa).

4. Chest imaging confirms lung involvement and inflammation.

5. Inflammatory status as documented by at least one of the following: Lactate dehydrogenase (LDH) > normal range, C-reactive protein (CRP)  $\geq$  100mg/L or IL-6  $\geq$  40pg/mL, serum ferritin  $\geq$  900ng/mL, XDP >20mcg/mL.

Patients randomized to the active treatment will receive an oral dose of reparixin (1200 mg tablets TID) for 7 days. In case of improvement, treatment can be prolonged at discretion of the investigator up to a total of 21 days of treatment. Patients randomized to the both arms will be offered, in case of worsening (e.g. need of ICU and/or mechanical ventilation), a rescue medication based on their physicians' judgement, without any constrain from the sponsor.

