#### 6.2 Control treatment

#### Phase 2/3 Control treatment

Control group in both the phase 2 and 3 segments will be standard of care, which due to the nature of the COVID-19 pandemic is expected to evolve over time and, thus, cannot be prespecified. This group will be populated in a prospective manner and offered a rescue medication in case of worsening (e.g. need of ICU and/or mechanical ventilation). Due to the evolving understanding of novel treatments being currently tested during the COVID-19 pandemic, the Sponsor will not put any restriction on the selection of the rescue medication during phase 2. In the phase 3, Reparixin will be offered as rescue medication, as oral tablets or as IV infusion in case of unfeasibility of the oral administration due to the clinical conditions (e.g. intubated patients in the ICU).

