#### **Dose and Route of Administration**

Oral tablets: For patients able to comply with the oral treatment, it is recommended to take for each administration two Reparixin 600 mg tablets, for the total of three daily administrations. It is advisable to take the tablets with a glass of water to facilitate swallowing. For patients who are unwilling or unable, in the opinion of the investigator, to comply with the oral tablets treatment, is possible to administration, disperse two Reparixin 600 mg tablets in 25 mL of drinking water in a suitable container (e.g. conical tubes for 50 mL Falcon centrifuge). Disgregate the tablets (shaking manually or with the aid of a planetary shaker or a rocker) until obtaining a homogeneous milky suspension (time required 7 - 10 minutes). Keep the prepared suspension at room temperature and protected from light for up to 24 hours. Immediately before administration, manually shake the suspension again until complete and homogeneous resuspension, withdraw using a 50 mL needle-free syringe and administer to the patient using a naso-gastric tube.

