#### **Dose and Route of Administration**

**IV infusion:** In the Phase 3, for patients randomized to the control arm who have worsened after 24hrs and within 14 days from randomization, Reparixin will be offered as rescue medication also as a continuous i.v. infusion into a central vein or dedicated peripherally inserted central catheter at a dose of 2.772 mg/kg body weight/hour for up to 7 days (120hrs).

The Reparixin solution for IV infusion will be provided by the Sponsor.

The dosing solution for infusion will be prepared at the designated Pharmacy or authorized location within each centre according to local guidelines for sterile re-consitution of i.v. injectable solutions. For each 750 mL dosing solution volume, the content of a Vial (250 mL) will be diluted with 500 mL of 0.9% sterile saline to dispense reparixin as 11.00 mg/mL solution. The dosing solution will be placed in a 1000 mL sterile empty Infusion Bag. Dosing solutions will be prepared and used within 72 hours from preparation, unless the site has more restrictive rules

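### Minor: the IV overdose line in Protocol 7.3.10 omits the word for excess, so read literally a correct Phase 3 rescue infusion becomes a reportable overdose after 12 hours

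*Protocol*

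**What the plan says.** Protocol section 7.3.10 makes any overdose, with or without a serious reaction, reportable to the sponsor by the SAE procedure within 24 hours of the investigator learning of it. It then defines overdose in two lines:

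- The oral line is "Tablets: The administration of 3 or more additional tablets on any given treatment day".
- The infusion line, which follows it, is "IV formulation: The administration of more than 50% of the daily dose".

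The dosing that these lines refer to is in section 6.3. Oral patients are to "take for each administration two Reparixin 600 mg tablets, for the total of three daily administrations". The IV product is a continuous infusion "at a dose of 2.772 mg/kg body weight/hour for up to 7 days".

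Sections 6.2 and 6.3 say who receives the infusion. In Phase 3, "Reparixin will be offered as rescue medication, as oral tablets or as IV infusion in case of unfeasibility of the oral administration", and the IV dosing text applies "for patients randomized to the control arm who have worsened after 24hrs and within 14 days from randomization". In Phase 2 the study drug is oral: "Patients randomized to the active treatment will receive an oral dose of reparixin (1200 mg tablets TID) for 7 days" (section 4.1). Phase 3 itself is provisional: "The Phase 3 design will be reassessed and decided based on the results of the Phase 2" (section 1, Overall Study Design).

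Neither the protocol nor the SAP contains another definition of overdose.

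**The concern.** An overdose definition should separate a dosing error from correct dosing. The tablet line does so because it counts additional tablets. The IV line gives a share of the daily dose without saying that the share is on top of the planned amount. As worded, a patient who has correctly received more than half of one day's infusion meets the definition.

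The definition triggers an expedited reporting duty. A site that applies it literally files an SAE-procedure report for a patient who was dosed as planned. A site that reads it sensibly replaces the written rule with its own. Two sites could therefore report the same infusion differently, and reports of correct dosing would sit among reports of real errors. The patients concerned are those too ill for oral treatment, for example intubated patients in the ICU.

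**Working it through.** **Inputs**
- IV rate: 2.772 mg/kg/h, continuous (Protocol 6.3, IV dosing).
- Tablets: 2 tablets of 600 mg, 3 times a day (Protocol 6.3, oral dosing).
- Tablet overdose threshold: 3 extra tablets in a day (Protocol 7.3.10).
- IV overdose threshold: more than 50% of the daily dose (Protocol 7.3.10).

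**Step 1. IV daily dose.** The protocol states no daily figure, so it is derived as rate × 24 h:

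2.772 × 24 = 66.528 mg/kg.

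Check: 48 h at the same rate gives 2.772 × 48 = 133.06 mg/kg, in line with the 133 mg/kg over 48 h given in Protocol 10.1.4.

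**Step 2. Literal threshold.**

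0.5 × 66.528 = 33.264 mg/kg.

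Time to reach it at the planned rate: 33.264 / 2.772 = 12.0 h. Any correct infusion longer than 12 h meets the definition. A full correct day delivers 100% of the daily dose, twice the literal threshold.

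**Step 3. What the tablet line implies.**

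Planned tablets: 2 × 3 = 6 per day. Threshold: 3 / 6 = 50% above the daily dose, or 9 tablets in total.

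**Step 4. The IV threshold on the same basis.** More than 50% above the daily dose:

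1.5 × 66.528 = 99.792 mg/kg for a full 24 h of planned infusion.

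Ratio to the literal threshold: 99.792 / 33.264 = 3.0. A correct day (66.528 mg/kg) is below this threshold and is not an overdose.

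**Step 5. Direction of the error.** Any total above 150% of the daily dose is also above 50% of it. The literal line therefore catches everything that the intended daily-total rule would catch, and in addition catches correct dosing. Its error is towards over-reporting.

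Section 6.3 prints the maximum duration as 7 days with 120 hours in brackets (7 × 24 = 168). The 12 h result does not depend on which is meant.

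**The case against.** The strongest answer is that nobody would apply the literal reading. The line stands under a heading on overdose, directly below a tablet rule that works out at +50%, and overdose means excess. Much of this stands. The intent can be inferred, and reports of correct infusions are a possible effect of the wording, not an expected one. The Investigator's Brochure, the SAE completion guideline and the pharmacy instructions are separate documents, not available here, and may make practice clear. What remains is that a definition should not lean on the everyday meaning of the word it defines, particularly when the line above states the excess explicitly and a 24-hour duty follows.

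Three stronger readings are tempting, and the documents do not support them.

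- A reader might infer that the IV line has no time frame at all. It lacks the tablet line's reference to a treatment day, but a daily dose is already a per-day quantity. The 12 h figure is the same either way. The real omission is the word for excess.
- A reader might infer that the line would let dangerous infusion errors through, because Protocol 10.1.4 describes severe gastrointestinal bleeding in a patient given three times the planned dose. That section reports a threefold dose and gives no infusion rate or duration, so it does not show that an infusion-rate error would be missed. The events were assessed as serious, and serious events are reportable within 24 hours under sections 7.3.1 and 7.3.6 whatever 7.3.10 says. Whether to add a rate criterion is a separate design question and not part of this point.
- A reader might infer that current patients or trial results are affected. Phase 2 study drug is oral. IV rescue is planned only for Phase 3, which depends on Phase 2 succeeding and, under SAP 4.7, on a protocol amendment first.

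**Conclusion.** The concern holds as a minor wording error. As written, the IV threshold is one third of the evident intent (33.3 against 99.8 mg/kg), and correct dosing passes it after 12 h. The wording itself is certain. The practical effect is unknown, because it depends on how sites read the line and on instructions not available here.

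The figures assume that the IV daily dose is 24 h at the stated rate, and that the IV line was meant to parallel the tablet line. The 99.8 mg/kg figure applies to a full day of infusion, not to a first or last part-day.

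The scope is safety reporting for control-arm patients given IV rescue in Phase 3, if that phase goes ahead with IV rescue. SAP 8.1 plans no overdose table, so no planned output changes. The primary analyses, power and type I error are untouched.

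**What to change.** In the Phase 3 protocol amendment, before any IV rescue is given, replace the IV line in section 7.3.10 with:

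*IV formulation: the administration of more than 50% above the planned daily dose on any given treatment day.*

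This supplies the missing excess, keeps the sponsor's strict inequality, and uses the same daily window as the tablet line. It needs no mg/kg figure in the text, so it stays valid if the Phase 3 regimen changes. The sponsor should confirm that +50% is the intended threshold and check that the SAE guideline and pharmacy instructions agree.

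The cost is one sentence in an amendment that SAP 4.7 already requires. No analysis or SAP table has to change.

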#### 7.4 Study Procedures and Randomization

Potential study patients with confirmed COVID-19 diagnosis will be identified from those hospitalized at the participating clinical sites for management of their COVID-19 associated severe pneumonia. Screening will be performed and completed in consented patients and potential study patients will be treated. All the subjects who sign the informed consent form for the present study and will be screened will be coded with "unique subject identifiers" (see section 10.5).

Each patient will be involved in the study for the entire duration of the hospital treatment and for a maximum of 31 days (one month) including the follow-up.

All the laboratory and clinical parameters, including radiography imaging assessments, will be collected based on the local procedures of the participating clinical sites.

The degree of dyspnea will be collected using the "Liker" and Visual Analogues (VAS) scales. The Liker scale is used as follows: the patient grades his current breathing compared to when he first started the drug (from -3 to 3). "0" = no change, "1" =minimally better, "2" =moderately better, "3" =markedly better, "-1" =minimally worse, "-2" =moderately worse, "-3" =markedly worse. The VAS scale is used as follows: the patient draws a horizontal line on an axial graph (from 0 to 100) to show the degree of how he feels about breathing. The number "0" equals the worst breathing the patient has ever felt and the number "100" equals the best he has ever felt.

Before randomization, and any study related procedures, at study entry all patients must have given a written informed consent for the study and must be assigned a screening number. In order to request randomization to the study, all the pre-treatment evaluations must be completed and all the inclusion and exclusion criteria satisfied.

Consecutive randomisation numbers will be given to the subjects upon their definitive enrolment in the study. Subjects will be assigned to their treatment according to their randomisation number. Patients will be randomized in a 2:1 fashion between Reparixin and standard treatment using a computer generated Randomization List generated by the Sponsor.

#### 8 END OF STUDY, DISCONTINUATION AND WITHDRAWAL

#### 8.1 End of study (EOS):

The EOS is defined as the last day the last patient completes the last study assessment in the hospital, or retracts the consent to participate in the study, or withdraws from the study, or is deceased or otherwise lost to follow-up.

#### 8.2 Discontinuation and Withdrawal

A patient has the right to withdraw from this clinical trial at any time and for any reason, without any repercussion.

The investigators also have the right to withdraw a patient from the study at any time if in their opinion it is no longer in the best interest of the patient to remain in the study.

As no withdrawals have been anticipated in the sample size calculations, patients who are withdrawn before completing the minimum of 24hrs treatment with the oral tablets in the active group can be replaced to reach the predefined samples size of the Phase 2 segment of the study. Participants who whitdraw from the study cannot be re-randomized.

Considerations on withdrawals for the Phase 3 segment of the study will be reassessed.

All discontinuations must be recorded by the investigators and reported to the Sponsor and, if possibile, an early discontinuation visit should be conducted and data recorded.

Temporary discontinuation or drug discontinuation is not allowed since treatment with the medication is planned for continuous use throughout the treatment phase.

Patients will be followed-up according to the study procedures set forth in this clinical trial protocol and until the scheduled last day of follow-up. The only exception will be the collection and reporting of AEs that have occurred during the clinical trial and have not resolved by the time of the end of follow-up: in this case AEs will be followed until resolution or stabilization.

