4.1 General

Appropriate descriptive statistics will be produced, according to the variable:

- for continuous data n , mean, standard deviation (SD), median, Q1-Q3, and range (minimum and maximum) will be presented;
- for categorical data, frequency distributions and percentages will be presented;
- for time-to-event variables, cumulative freedom from event will be evaluated using Kaplan-Meier (KM) method. The degree of uncertainty will be expressed with 95% confidence limits (calculated per the method proposed by Greenwood³). Comparison of curves among arms will be performed with the log-rank test. KM graphs will be presented along with the number of subject-at-risk at exact time points. Subjects who have discontinued/terminated the study without an event will be censored at the date of study discontinuation/termination. Subjects ongoing and who are free from event at the time of database lock (for example at interim analyses) will be censored at the last available date.

Unless otherwise specified, hypothesis testing will be carried out at the $\alpha = 0.050$ level (two-sided) when comparing treatments. For all inferential analyses, p-value will be rounded to three decimal places. Statistical significance will be declared if the rounded p-value will be less than or equal to 0.050. For primary analysis only (section 7.1.2), p-values will be provided at 5th decimal place, in order to compare with efficacy and futility thresholds specified in section 4.5.

Additional post-hoc analysis may be produced to further allow comparison between reparixin and control, according to the results obtained. Any unplanned analyses as well as deviations from the original statistical plan will be clearly documented in the Clinical Study Report.

Derivation rules for efficacy and safety analyses are reported in Table 7 in section 9.

All the data collected and derived in the study will be presented in subject data listings by centre.

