4.2.4 Full Analysis set

The Full Analysis Set (FAS) will consist of all randomized subjects who receive at least one dose of the IMP. FAS population will be analyzed according to ITT principle, i.e. by treatment allocation regardless happening of intercurrent events. The FAS population will be used for the primary analyses of the study and to present results on efficacy data.

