5.3 Study discontinuations

The following information will be summarized by treatment and overall:

- Trial completers;
- Subjects who discontinued the IMP (and reasons);
- Subjects who discontinued the trial prematurely (and reasons);
- Subjects who discontinued the IMP but complete the study;
- Subjects who discontinued the IMP and discontinued the trial prematurely.

If more than 30% of randomized subjects discontinue the study prematurely, the distribution of the time from randomization to discontinuation will be summarized using time-to-event method. Subjects who have not prematurely discontinued the trial will be censored at study termination.

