8.1 Adverse events

Any AE which starts at or after the first administration of study treatment will be considered a Treatment Emergent Adverse Event (TEAE). Pre-treatment AEs and TEAEs will be presented separately. Pre-treatment AEs will be presented in the listings only. In case of missing or incomplete dates not allowing a direct allocation to any of the two categories of AEs, a worst-case allocation will be done according to the available parts of the onset and the end dates (see Table 8). The AE will be allocated to the first category allowed by the available data, according to the following order:

- TEAE;
- Pre-treatment AE.

All AEs will be assigned to a PT and will be classified by primary SOC according to the MedDRA thesaurus. In addition, each AE will be graded according to severity definitions as “Mild”, “Moderate” or “Severe”.

TEAEs will be reported on a per-subject basis, i.e. if a subject reported the same event repeatedly (i.e. events mapped to the PT) the event will be counted only once.

For summaries, the drug-event relationship will be assessed as “None”, “Unlikely”, “Possible” “Probable” or “Highly probable”. Any TEAE reported in the study having a possible, probable or highly probable relationship to IMP will be defined as “Adverse Drug Reaction” (ADR).

The following tables and listings will be presented by treatment group:

- An overview of TEAEs including the number of subjects who exhibited at least one TEAE, at least one severe TEAE, at least one serious TEAE, at least one non-serious TEAE, at least one ADR, at least one serious ADR, number of TEAEs, number of non-serious TEAEs, number of TESAEs, number of ADRs, number of serious ADRs, number of deaths, number of subjects who temporarily interrupted IMP due to a TEAE, number of subjects who permanently interrupted IMP due to a TEAE;
- Summary of TEAEs by primary SOC and PT;
- Summary of TEAEs by primary SOC, PT and Severity;
- Summary of Serious TEAEs by Primary SOC and PT;
- Summary of ADRs by Primary SOC and PT;
- Summary of ADRs by Primary SOC and PT and Severity;
- Summary of TEAEs leading to IMP temporary interruption by Primary SOC and PT;
- Summary of TEAEs leading to IMP permanently interruption by Primary SOC and PT;
- Summary of TEAEs leading to Death by Primary SOC and PT;
- Listing of all AEs by Subject;
- Listing of SAEs by Subject;
- Listing of ADR by Subject;
- Listing of Deaths.

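### Protocol 8.2 bars pausing or stopping study drug with no safety exception, while the SAP plans for patients who do so and stay in the study (phase 2, minor)

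*Protocol*

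**What the plan says.** **Protocol.** Section 8.2 reads: "Temporary discontinuation or drug discontinuation is not allowed since treatment with the medication is planned for continuous use throughout the treatment phase". Continuous use is the only reason given, and no exception follows. The sentence does not use the word permanent; reading its second limb as a permanent stop is natural, but it is a reading. The same section offers an exit in the patient's interest, but from the study: "The investigators also have the right to withdraw a patient from the study at any time". The heading of 7.3.9 speaks of adverse events that cause treatment to stop. Its text covers only a patient withdrawn from the study, and requires that "the patient must be followed up until the resolution of the AE or as instructed by the medical monitor", without mentioning the primary endpoint. Section 7.3.8 removes a pregnant patient from the trial. Section 9.4.1 censors event-free patients at discontinuation, without saying whether of drug or of study.

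**SAP.** Section 5.3 has a disposition row for "Subjects who discontinued the IMP but complete the study", separate from patients who stopped both. Section 8.1 reports the "number of subjects who permanently interrupted IMP due to a TEAE", the matching count for temporary interruption, and a "Summary of TEAEs leading to IMP temporary interruption by Primary SOC and PT". Section 4.2.4 analyses the full analysis set "by treatment allocation regardless happening of intercurrent events". Section 4.1 is specific about censoring: "Subjects who have discontinued/terminated the study without an event will be censored at the date of study discontinuation/termination". Section 4.9 declares no change to the planned analysis.

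**The concern.** The two documents describe different trials for a patient who develops toxicity during the fixed 7-day course. Under the protocol, the site either departs from 8.2 or takes the patient out of the study. Under the SAP, the patient can come off drug, complete the study and be counted.

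Two things are at stake. The first is safety: stopping a drug for toxicity should not require a protocol deviation or the loss of the patient from the trial. The second is retention of outcome data: an event-free patient who is withdrawn is censored on that day, although the SAP means to analyse by allocation whatever happens to treatment. Toxicity is foreseeable. Protocol 10.1.4 reports grade 3 reactions with the oral tablets, one grade 4 reaction, and one further patient with grade 4 peritonitis and grade 5 intestinal perforation.

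**Working it through.** **1. Ways off drug, set side by side**

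| Situation | Protocol | SAP |
|---|---|---|
| Temporary pause for an adverse event | Not allowed (8.2) | Counted and tabulated (8.1) |
| Permanent stop for an adverse event, patient stays | Not allowed on the natural reading of 8.2; no other section provides for it | Row in 5.3; count in 8.1, which does not say whether the patient stays |
| Withdrawal from the study | Allowed (8.2, 7.3.9) | Censored if event-free (4.1) |

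The protocol's exits all lead out of the study. Dosing after day 7 is at the investigator's discretion (protocol 4.1), so the conflict bites in the first 7 days.

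**2. What each course of action does to the phase 2 analysis**

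- *The site withdraws the patient.* If event-free, the patient is censored at that date (protocol 9.4.1, SAP 4.1).
- *The site stops drug, records a deviation and keeps the patient.* The patient stays in the full analysis set by allocation (SAP 4.2.4) and is not censored, because SAP 4.1 censors only at study discontinuation. The per-protocol comparison is listed for phase 3 (SAP 7.1.3.2) and not for phase 2 (SAP 7.1.3.1); protocol 9.4.2.4 also places it at the phase III analysis. No phase 2 primary or sensitivity analysis changes.

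**3. An illustrative number of stops**

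Neither document gives a stopping rate. From the oral-tablet data in protocol 10.1.4:

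- Grade 3 reactions: 0.043 × 505 = 21.7, about 22.
- Add one grade 4 reaction and the one patient with grade 4 and 5 reactions: 22 + 1 + 1 = 24.
- If each fell in a different patient: 24/111 = 21.6%, and 0.216 × 32 = 6.9, about 7 reparixin patients.
- Low end: 0, in line with the IV islet trials, where none of the most frequent reactions required stopping.

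Seven is not a bound. The listed grades sum to 70.9 + 22.9 + 4.3 = 98.1%, so 0.019 × 505 = 9.6, about 10 reactions, lie outside grades 1 to 3, and only two units were added for them. In the other direction, 505/78 is about 6.5 reactions per affected patient, so severe reactions probably cluster. The source is also indirect: all 111 patients had breast cancer, 30 + 61 = 91 also received paclitaxel, and the oral trials dosed in 21-day cycles.

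**4. Effect on power**

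Inputs: medians of 2 and 5 days (SAP Table 2), 16 control and 32 reparixin patients, exponential times, 21 days of follow-up, one-sided 0.025, fixed design, uninformative withdrawal.

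Reproducing the plan first:

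- Expected events = 32 × (1 − 2^(−21/5)) + 16 × (1 − 2^(−21/2)) = 30.26 + 15.99 = 46.25. The SAP has 46.
- Schoenfeld power = Φ(√(46.25 × 2/9) × ln 2.5 − 1.96) = Φ(0.98) = 0.836. The SAP says approximately 80%, with an interim analysis that is not modelled here.

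Then 20,000 simulated trials per case, with k reparixin patients censored at day d if still event-free (Monte Carlo standard error about 0.003):

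| k | Day d | Mean events | Log-rank power |
|---|---|---|---|
| 0 | – | 46.3 | 0.834 |
| 1 | 3 | 45.6 | 0.827 |
| 3 | 3 | 44.4 | 0.829 |
| 7 | 3 | 42.0 | 0.815 |
| 7 | 1 | 40.5 | 0.803 |

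The last row is pessimistic, because 8.2 allows replacement of active-group patients withdrawn before 24 hours of treatment.

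**The case against.** The strongest reply is that this is one loosely worded sentence in a section that otherwise handles discontinuation. The sentence before it requires all discontinuations to be recorded, with an early visit if possible; the one after it follows patients to the scheduled last day. Section 7.3.3 records the action taken for each adverse event, 7.3.5 makes the investigator responsible for safe care, and SAP 4.6 lists medication discontinuations among the items for the monitoring committee. The ban may be aimed at elective pauses, since earlier oral trials had a 7-day drug holiday after each 21 days (protocol 10.1.3). The SAP rows may simply tabulate whatever happens, deviations included.

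Much of this lowers the stakes, but it does not remove the clash. The recording duties and the general duty of care do not grant permission to stop drug. The follow-up sentence does not say that withdrawn patients stay in follow-up for the endpoint. The narrower reading is inference, and the sentence bars drug discontinuation as well as temporary discontinuation. The SAP does not label its rows as deviations, and having to record a deviation to stop a drug for toxicity is itself the defect.

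Three stronger readings are tempting and are not supported:

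- *Patients are held on a harmful drug.* They are not: the investigator may withdraw a patient at any time.
- *Only the reparixin arm can lose patients this way, so the comparison is biased.* Withdrawal for an adverse event or in the patient's interest is open to both arms (8.2, 7.3.9). Protocol 9.3 counts standard of care as investigational product, and SAP 5.4 tracks its continuation. The ban bears mainly on reparixin, but censoring at withdrawal is not exclusive to it.
- *Power is at risk.* The simulation shows no material loss.

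**Conclusion.** The conflict holds as a matter of text: 8.2 states a prohibition with no safety exception, and SAP 5.3, 8.1 and 4.2.4 presuppose patients who pause or stop drug and remain under observation. Confidence in the clash of wording is high; confidence in any practical consequence is lower. Censoring follows only where the site chooses full withdrawal. A bias cannot be sized or signed without a stopping rate and the prognosis of those who stop, and the power result assumes that withdrawal is unrelated to prognosis. The finding is limited to phase 2, because protocol 8.2 leaves phase 3 withdrawals to be reassessed and SAP 4.7 requires a protocol amendment before phase 3. Severity is minor. The reason to act is safety and retention.

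**What to change.** Amend protocol 8.2 to permit interruption or permanent stop of study drug for safety, on clinical criteria set by the sponsor and investigators, with the patient remaining in scheduled follow-up for the primary endpoint unless consent is withdrawn. As a consistency edit, align protocol 9.4.1 with SAP 4.1: censoring is at study discontinuation, and stopping drug alone does not censor.

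The cost is a wording amendment to 8.2 and one line in 9.4.1. SAP 4.1, 4.2.4, 5.3 and 8.1 already fit the amended text, and no visits are added to the existing schedule. The documents do not say whether phase 2 dosing is complete, though SAP 4.9 speaks of enrolled patients in the past tense. If it is complete, the amendment helps only later patients, and the SAP or study report should state how drug stops in phase 2 were handled.
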